**1st or 2nd Infusion Interruption:**

- Hold infusion and closely monitor subject, institute symptomatic medical management until resolution of IRR symptoms.
- Following the judgment of the Investigator, and provided the subject is stable, the infusion may be resumed at no more than half the previous rate.
- If the subject does not experience any further IRR symptoms, infusion rate escalation may resume at the increments and intervals as appropriate at the treatment cycle dose (see Section 6.2.1.2).

**3rd Infusion Interruption (same day):**

- Discontinue infusion for that day – monitor subject for resolution of all symptoms. Subject should have all vital signs completed as well as any other standard of care procedures completed as warranted by the Investigator prior to release of subject from study site.
- Any remaining diluted investigational product should be discarded.

If the infusion discontinued is the Cycle 1 Day 1 infusion, administer the scheduled Cycle 1 Day 2 dose according to the protocol dosing schedule.

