	
minutes prior to the beginning of the ublituximab infusion. After Cycle 1, adjustments may be made to the antihistamine and/or corticosteroid dosing if deemed medically necessary. Please contact TG Therapeutics with any questions.
 
Ublituximab infusion in Cycle 1 only is split between Day 1 and Day 2, with the subject receiving up to 150 mg on Day 1 and remainder of the dose on Day 2 for subject crossing over from UTX-TGR-304 Arms B and D
 
For all subjects at risk for tumor lysis syndrome in the opinion of the treating investigator, prophylaxis with allopurinol or per recommended institutional standards should be considered.

Study Drugs	
Ublituximab is a glycoengineered, recombinant chimeric monoclonal antibody against the CD20 antigen, available as a 10 mg/mL or 25 mg/mL concentrate for solution for infusion, supplied by TG Therapeutics, Inc.
 
Umbralisib (TGR-1202) is a highly specific and orally available PI3K delta (<math>\delta</math>) inhibitor available in 200 mg tablets, supplied by TG Therapeutics, Inc.

Statistical Considerations	
Subjects from Treatment Arms B, C and D in Study 304 may enter this study upon documented progression of disease as confirmed by the independent central radiology review group. At the end of Study 304, non-progressed subjects from Treatment Arm A may also be enrolled to this Phase 2 Companion Study. It is undetermined the number of subjects that may enter this Companion Study, however it may not exceed the total number of subjects that have enrolled in Study 304.
 
As this study is intended as a compassionate use study for subjects progressing on Study 304, no formal hypothesis testing will be conducted. Efficacy and safety may be presented descriptively with subjects grouped by the treatment that the subjects received during the UTX-TGR-304 protocol prior to entering the Companion Study and overall.

Estimated Study Duration	
This study will remain open as long as there are subjects enrolling or who have been enrolled to Study UTX-TGR-304.

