 Unilateral bone marrow aspirate and/or biopsy performed at investigator discretion in subjects for whom assessment of extent of CLL involvement and bone marrow cellularity is important. In addition, a post-baseline bone marrow biopsy should be completed to confirm potential CR by radiological assessment.

 For women of child bearing potential, completed within 3 days of Cycle 1 Day 1.

 For women of child bearing potential, completed within 3 days of visit

 Must be obtained prior to ublituximab administration if on day of infusion.

 Must be done within 14 days of cycle 1 day 1

 For del(13q), del(11q), del(17p), and (12) trisomy, t(11:14)

 Scans should be completed approximately 45 days prior to Day 1 of Cycle 1. Radiology assessment should include CT or MRI imaging of chest, abdomen, and pelvis.

 Serum virology to include HBsAg, HbC antibody, HCV antibody and CMV IgG and IgM. If HbC antibody, HCV antibody or CMV IgM is positive, subjects must be evaluated for the presence of active HBV, HCV or CMV by PCR

 Q3 months CMV screening by PCR for all subjects.

 Peripheral blood sample may be analyzed by local lab. For subjects MRD negative by peripheral blood, a bone marrow should be completed to confirm MRD negativity. If a bone marrow is not completed, another peripheral blood sample should be collected to confirm the MRD negativity at least 12 weeks later. MRD should continue to be evaluated for subjects with PR/CR at response assessment intervals until 2 consecutive peripheral blood MRD negative results, or 1 negative peripheral blood MRD and 1 negative bone marrow MRD are observed.

 Subjects who received ublituximab on UNITY-CLL trial (Arm C), will not receive split dosing on Day 1 and 2 of cycle 1. Subjects should receive full dose on Cycle 1, Day 1 and will not receive Day 8, and 15 during Cycle 1.

 If clinically significant adverse event or abnormal result is observed that is not resolved by the end-of treatment visit, continue to monitor and record up through 30 days after study drug discontinuation.

TABLE 2: FOLLOW UP ASSESSMENTS SCHEDULE

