**6.2.1.2 FLOW RATE RECOMMENDATIONS FOR UBLITUXIMAB ADMINISTRATION**

**Cycle 1 Day 1 & 2 infusion over 4 hours**

Cycle 1	Ublituximab Dose	Total volume to be infused	Infusion rate			
			T0 to T30'	T30' to T1H	T1H to T2H	T2H to T4H
Day 1	150 mg	250 mL	10 mL/H	20 mL/H	35 mL/H	100 mL/H
Day 2	750 mg	500 mL	10 mL/H	20 mL/H	85 mL/H	200 mL/H

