### 6.4.1 DOSE DELAY: UBLITUXIMAB

No reduction in the dose of ublituximab is permitted. Please refer to [Section 6.2.1.2](#) for detailed information on infusion rate guidance for infusion related reactions related to ublituximab.

Supportive care should be considered for any subject who experiences Grade  $\geq 2$  cytopenias, or Grade  $\geq 1$  non-hematologic toxicities. Delay of both study drugs (individually or together) is allowed for recovery of hematologic toxicities to  $\leq$  Grade 3 or non-hematologic toxicities to  $\leq$  Grade 2 or to baseline level. If delay is greater than 2-cycles, notify TG Therapeutics prior to re-initiating with any questions. If the subject withdraws consent or has documented progression, an end of study visit should be completed.

If a subject discontinues only one study drug (either ublituximab or umbralisib), the subject may continue treatment with the other study drug per the protocol.

TABLE 3: DOSE DELAY GUIDELINES: UBLITUXIMAB

NCI-CTCAE Grade	Dose Delay and/or Modification
Hematologic Adverse Event	
Neutropenia	
Grade $\leq 3$ neutropenia	Maintain current dose. Consider supportive care as warranted.
Grade 4 neutropenia or occurrence of neutropenic fever or infection	Delay ublituximab until Grade $\leq 3$ and/or neutropenic fever or infection is resolved; consider growth-factor support as warranted; thereafter, resume at full dose.
Thrombocytopenia	
Grade $\leq 3$ thrombocytopenia	Maintain current dose level and provide supportive care as clinically warranted.
Grade 4 thrombocytopenia	Delay ublituximab until Grade $\leq 3$ ; consider intervention with supportive care as warranted; thereafter resume at full dose.
Non-Hematological Adverse Events	
Grade $\leq 2$	Maintain current dose level
Grade $\geq 3$	Withhold ublituximab until Grade $\leq 2$ at the discretion of the investigator; consider supportive

	care intervention as warranted. Resume at full dose.
--	--

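### The rule for a stopped Cycle 1 Day 1 ublituximab infusion refers every arm to a Day 2 dose, but the documents disagree on whether Arm C has one, and the synopsis wording for Arms B and D is ambiguous

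*Combined protocol and SAP*

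**What the plan says.** Section 6.2.1.1, under the third same-day interruption, ends the infusion for that day and adds: "Any remaining diluted investigational product should be discarded". It continues that, where the abandoned infusion is that of Cycle 1 Day 1, the site is to "administer the scheduled Cycle 1 Day 2 dose according to the protocol dosing schedule". Neither sentence mentions a treatment arm.

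For Arms B and D, the synopsis table, the Section 6.1 schema, the flow-rate table in Section 6.2.1.2 and the dilution table in Section 6.2.1.3.1 all print 150 mg on Day 1 and 750 mg on Day 2. The synopsis text below its table describes the split differently, "with the subject receiving up to 150 mg on Day 1 and remainder of the dose on Day 2 for subject crossing over" from Arms B and D.

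For Arm C, Section 6.1 lists 900 mg on Day 1 of Cycles 1 to 6 and no Day 2 dose. Table 1 footnote 15 rules out the split for this arm and adds: "Subjects should receive full dose on Cycle 1, Day 1 and will not receive Day 8, and 15 during Cycle 1". The synopsis, however, introduces its dosing table, with 750 mg on Day 2, as the schedule for Arms B, C and D.

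**The concern.** The rule applies to a subject who has just had three interruptions in one day, when the site needs a single answer by the next morning. For Arm C it refers the site to a scheduled dose that two places do not contain and a third appears to contain. For Arms B and D it fixes Day 2 at the scheduled amount, whereas the synopsis can be read as making Day 2 depend on what was infused on Day 1.

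If sites read these places differently, subjects with the same event get different Day 2 amounts. Section 6.2.1.3 requires the exact dose to be recorded, so the Section 9.7 exposure summary would show what was given. It could not show whether a difference came from the subject's reaction or from the page the site followed. The same doubt affects which Cycle 1 doses count as protocol deviations when the Per-Protocol population in Section 9.3 is defined.

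**Working it through.** **Inputs.** Day 1 is 150 mg in 250 mL and Day 2 is 750 mg in 500 mL, with the stepped rates in Section 6.2.1.2. Arm C receives 900 mg on Day 1 (Section 6.1). Let x be the mg delivered on Day 1 before the infusion is abandoned.

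**Reproducing the plan's figures.** Volume is the sum of rate × time.

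- Day 1: 0.5×10 + 0.5×20 + 1×35 + 2×100 = 5 + 10 + 35 + 200 = 250 mL.
- Day 2: 0.5×10 + 0.5×20 + 1×85 + 2×200 = 5 + 10 + 85 + 400 = 500 mL.
- Split total: 150 + 750 = 900 mg.

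The printed volumes and the four-hour duration are reproduced.

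**Arms B and D.** The two readings of Day 2 are:

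- undelivered balance: 900 − x mg;
- scheduled dose, or remainder read as nominal: 750 mg.

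Difference = (900 − x) − 750 = 150 − x mg. It is 0 when Day 1 was completed (x = 150) and approaches 150 mg as x approaches 0. The upper limit is 150/900 = 16.7% of the split total.

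To illustrate, assume the table rates run with no earlier hold. The Day 1 concentration is 150/250 = 0.6 mg/mL.

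| Stopped at | Volume given | x | 900 − x | Difference from 750 | % of 900 |
|---|---|---|---|---|---|
| 1 h | 15 mL | 9 mg | 891 mg | 141 mg | 15.7 |
| 2 h | 50 mL | 30 mg | 870 mg | 120 mg | 13.3 |
| 3 h | 150 mL | 90 mg | 810 mg | 60 mg | 6.7 |

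That assumption does not describe a real third interruption, which follows two holds, each resumed at no more than half the previous rate. Holds and slower rates reduce x at a given clock time. The formula is unchanged, so the supported statement is the range from 0 to just under 150 mg.

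The Day 2 row of the flow-rate table covers 750 mg in 500 mL only. A Day 2 dose of 900 − x mg would have no printed volume or rate.

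**Arm C.** Side by side:

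| Place | Day 2 dose for Arm C |
|---|---|
| Section 6.1, Arm C schema | none |
| Table 1, footnote 15 | none (split excluded) |
| Synopsis text on the split | none (split limited to Arms B and D) |
| Synopsis dosing table, as labelled | 750 mg |
| Section 6.2.1.1, third interruption | whatever is scheduled; no arm named |

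A site following Section 6.1 or footnote 15 finds nothing to give on Day 2, and the next scheduled ublituximab is Cycle 2 Day 1. A site following the synopsis table finds 750 mg. The Cycle 1 Day 1 rows in Sections 6.2.1.2 and 6.2.1.3.1 are for 150 mg, so Arm C's 900 mg Day 1 infusion is not carried through those tables either.

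**The case against.** The strongest reply is that only Section 6.2.1.1 addresses a stopped infusion, and it does so explicitly. The synopsis sentence mentions no interruption and states no 900 mg total, and the table above it prints 750 mg. A reader might infer that the documents hold two explicit, opposing rules for the same event in Arms B and D. They do not: remainder can mean the nominal 750 mg. This part of the reply stands, and it reduces the Arms B and D point to an ambiguity.

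A reader might also take the sentence "No reduction in the dose of ublituximab is permitted" in Section 6.4.1 as settling the matter in favour of the balance reading. It does not. It belongs to the toxicity dose-delay guidance, and the sentence after it refers infusion reactions back to Section 6.2.1.2. An infusion cut short is not clearly a prescribed reduction.

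For Arm C, a reader might infer that the rule leads to more than the planned 900 mg. Giving 750 mg after a partial infusion would exceed 900 mg only if x were above 150. The documents give no value of x, and footnote 15 excludes the split. The reply that an unscheduled dose leaves the rule with nothing to act on is fair under Section 6.1 and footnote 15. It does not answer the synopsis table's Arm C label, and it still leaves a stopped 900 mg infusion without instructions.

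The 52% infusion-reaction figure in Section 1.5 should not be used as a frequency here. It counts all such reactions in 27 subjects of another study on a different schedule.

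Finally, Section 6.2.1.1 calls its guidance recommended and leaves rate changes, delay and discontinuation to the investigator. That discretion does not extend to the Day 2 amount, for which the section gives a specific direction.

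**Conclusion.** The point holds in this form. For Arm C there is a real contradiction: the synopsis table's label gives the arm a 750 mg Day 2 dose, while Section 6.1, footnote 15 and the synopsis text on the split do not. The third-interruption rule depends on that unresolved question. For Arms B and D there is an ambiguity worth between 0 and just under 150 mg on Day 2, at most 16.7% of 900 mg. That size rests on reading remainder as the undelivered balance and on taking 150 + 750 as the total; on the nominal reading it is zero.

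How often this arises is unknown, because the documents give no rate of third interruptions. Sections 9.1 and 9.2 plan no hypothesis test, so no power or error rate is affected. What is affected is the consistency of Cycle 1 dosing after a reaction, the exposure summary and the classification of deviations. This warrants correction at the next amendment. No view is taken on which dose or rule is right.

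**What to change.** Reconcile the synopsis dosing table and the split-dose sentence below it, Table 1 footnote 15, the Section 6.1 schemas, the third-interruption rule in Section 6.2.1.1, and the tables in Sections 6.2.1.2 and 6.2.1.3.1, so that:

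- one rule states what is given after an incomplete Cycle 1 Day 1 infusion in Arms B and D;
- a separate rule states the same for Arm C;
- the arm label on the synopsis table agrees with Section 6.1, or Section 6.1 with the label;
- the volume and rate tables cover every dose the chosen rules allow, including Arm C's Day 1.

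The sponsor's clinical team must choose the content of the rules. The cost is a few sentences in the next amendment and in the pharmacy instructions, with no added subjects, procedures or staff.

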**6.2.1.2 FLOW RATE RECOMMENDATIONS FOR UBLITUXIMAB ADMINISTRATION**

**Cycle 1 Day 1 & 2 infusion over 4 hours**

Cycle 1	Ublituximab Dose	Total volume to be infused	Infusion rate			
			T0 to T30'	T30' to T1H	T1H to T2H	T2H to T4H
Day 1	150 mg	250 mL	10 mL/H	20 mL/H	35 mL/H	100 mL/H
Day 2	750 mg	500 mL	10 mL/H	20 mL/H	85 mL/H	200 mL/H

**Cycle 1 Day 8 & 15 infusions over 3 hours**

Ublituximab Dose	Total volume to be infused	Infusion rate		
		T0 to T1H	T1H to T2H	T2H to T3H
900 mg	500 mL	50 mL/H	150 mL/H	300 mL/H

**Cycle 2 and remaining infusions over 90 minutes**

Ublituximab Dose	Total volume to be infused	Infusion rate	
		T0 to T30min	T30min to T90min
900 mg	500 mL	200 mL/H	400 mL/H

**6.2.1.3 DISPENSING OF UBLITUXIMAB**

Before dispensing, the site pharmacist or his/her representative must check that the ublituximab is in accordance with the product specifications and the validity is within the re-test date.

The exact dose and the date and time of administration of ublituximab must be recorded within the eCRF, subject's medical records, and/or in the drug accountability records.

The Pharmacist or his/her representative should record the date dispensed and subject's number and initials, as well as complete the accountability record in the electronic drug accountability system with information concerning the dispensation of ublituximab. Preparation should be done by the Pharmacist or his/her representative according to instructions for sterile dilution.

#### 6.2.1.3.1 DILUTIONS OF UBLITUXIMAB

Ublituximab should not be mixed with other medicinal products. Ublituximab should only be diluted in 0.9% NaCl before use.

##### Dilutions for Cycle 1 Day 1 & Day 2

Dose of ublituximab for infusion	
Cycle 1 Day 1: 150 mg	
Cycle 1 Day 2: 750 mg	

##### Dilutions for $\geq$ Cycle 1 Day 8 Infusions

Dose of ublituximab for infusion	
900 mg	

##### Dilutions for Cycle 1 Day 1 & Day 2

Dose of ublituximab for infusion	
Cycle 1 Day 1: 150 mg	
Cycle 1 Day 2: 750 mg	

##### Dilutions for $\geq$ Cycle 1 Day 8 Infusions

Dose of ublituximab for infusion	
900 mg	

## 6.2.2 GUIDELINES FOR ADMINISTRATION OF UMBRALISIB (TGR-1202)

- *Method of Administration:* Umbralisib will be administered orally once daily with food
- *Potential Drug Interactions:* No Drug Interactions have been reported to date.

- *Pre-medications:* Subjects are required to start prophylaxis treatment with pneumocystis jiroveci pneumonia (PJP) and antiviral therapy prior to Cycle 1, Day 1, and must continue through Cycle 2, and per investigator discretion afterward. Choice of PJP and anti-viral prophylaxis therapy is per investigator discretion, with the below recommendations:
  - Anti-viral Prophylaxis: Valtrex 500 mg daily or Acyclovir 400 mg BID or equivalent
  - PJP Prophylaxis: Dapsone 100 mg daily or equivalent.

If anti-viral or anti-bacterial prophylaxis is not tolerated, we recommend alternating to a different prophylactic agent, reducing the dose or modifying the schedule for the prophylactic agent, or discontinuing prophylaxis at investigator discretion. Final choice of PJP and anti-viral prophylaxis therapy is per investigator discretion.

TGR-1202 will be dispensed at the sites by the research coordinator or designee under the direction of the PI or by a pharmacist at the site. Subjects must be provided drug in its original container. Subjects should be instructed to return any unused tablets when they return the bottle to the site. Study drug compliance should be reviewed with the subject at the beginning of each new treatment cycle and as needed. Missed doses will be documented in the subjects' medical record.

Umbralisib will be self-administered (by the subject). Tablets should be taken at approximately the same time each day with food (within 30 minutes of a meal). Subjects should be instructed to swallow the tablets whole and should not chew or crush them.

If a dose of umbralisib is missed, it should be taken as soon as possible on the same day. If it is missed for a period greater than 12 hours, it should not be replaced. If vomiting occurs, no attempt should be made to replace the vomited dose.

#### 6.2.2.1 DISPENSING OF UMBRALISIB

---

Before dispensing, the site pharmacist or his/her representative must check that the umbralisib is in accordance with the product specifications and the validity is within the re-test date.

The exact dose and the date of administration of umbralisib must be recorded within the eCRF, subject's medical records, and/or in the drug accountability records. For the purpose of drug accountability and dosing, subjects should record any missed doses of umbralisib on a drug diary. Any error in drug administration should be recorded (e.g., missed dose) in the eCRF

The Pharmacist or his/her representative should record the date dispensed and subject's number and initials, as well as complete the accountability record in the electronic drug accountability system with information concerning the dispensation of umbralisib.

### 6.3 CRITERIA FOR ONGOING TREATMENT

---

Continue treatment as per protocol provided that subject has:

- No intolerable toxicities related to study drug.
  - If treatment is delayed greater than 2 cycles, notify TG Therapeutics prior to re-initiation.
- No clinical or radiographic evidence of disease progression.
- Not withdrawn from the study for other reasons.

## 6.4 DOSING DELAYS/DOSE MODIFICATION

Subjects should be assessed clinically for toxicity at each visit using the NCI CTCAE v4.0 ([http://evs.nci.nih.gov/ftp1/CTCAE/CTCAE\\_4.03\\_2010-06-14\\_QuickReference\\_8.5x11.pdf](http://evs.nci.nih.gov/ftp1/CTCAE/CTCAE_4.03_2010-06-14_QuickReference_8.5x11.pdf)) grading scale. Dose delay and/or modification guidance is for adverse events considered at least possibly related to the study drug. If cytopenias are deemed related to the underlying disease rather than study drug, dose modifications are not required, or are per investigator discretion.

If greater than 2-cycle delay of treatment occurs for recovery of toxicities as outlined in Section 6.4 DOSING DELAYS/DOSE MODIFICATION, re-initiation of treatment is at the discretion of the investigator. Contact TG Therapeutics prior to re-initiating treatment with any questions. If a subject discontinues treatment due to toxicity, then the subject should continue to be followed for progression as described in [Table 2: FOLLOW UP ASSESSMENTS SCHEDULE](#). If a subject withdraws consent or has documented progression, an end of study visit should be completed.

### 6.4.1 DOSE DELAY: UBLITUXIMAB

No reduction in the dose of ublituximab is permitted. Please refer to [Section 6.2.1.2](#) for detailed information on infusion rate guidance for infusion related reactions related to ublituximab.

Supportive care should be considered for any subject who experiences Grade  $\geq 2$  cytopenias, or Grade  $\geq 1$  non-hematologic toxicities. Delay of both study drugs (individually or together) is allowed for recovery of hematologic toxicities to  $\leq$  Grade 3 or non-hematologic toxicities to  $\leq$  Grade 2 or to baseline level. If delay is greater than 2-cycles, notify TG Therapeutics prior to re-initiating with any questions. If the subject withdraws consent or has documented progression, an end of study visit should be completed.

If a subject discontinues only one study drug (either ublituximab or umbralisib), the subject may continue treatment with the other study drug per the protocol.

TABLE 3: DOSE DELAY GUIDELINES: UBLITUXIMAB

NCI-CTCAE Grade	Dose Delay and/or Modification
Hematologic Adverse Event	
Neutropenia	
Grade $\leq 3$ neutropenia	Maintain current dose. Consider supportive care as warranted.
Grade 4 neutropenia or occurrence of neutropenic fever or infection	Delay ublituximab until Grade $\leq 3$ and/or neutropenic fever or infection is resolved; consider growth-factor support as warranted; thereafter, resume at full dose.
Thrombocytopenia	
Grade $\leq 3$ thrombocytopenia	Maintain current dose level and provide supportive care as clinically warranted.
Grade 4 thrombocytopenia	Delay ublituximab until Grade $\leq 3$ ; consider intervention with supportive care as warranted; thereafter resume at full dose.
Non-Hematological Adverse Events	
Grade $\leq 2$	Maintain current dose level
Grade $\geq 3$	Withhold ublituximab until Grade $\leq 2$ at the discretion of the investigator; consider supportive

	care intervention as warranted. Resume at full dose.
--	--

